01.12.2024

Comparative Evaluation of the Possible Effects of Platelet Rich Plasma (Prp) and Low Level Laser (Biolase) on Postoperative Complications and Wound Healing After Extraction of Impacted Wisdom Teeth

Study Protocol

The study was conducted on a total of 30 patients aged between 18 and 40 years who applied to the XXX Oral and Maxillofacial Surgery Department Clinic for bilateral, similar position, half mucosa and bone retention lower impacted wisdom teeth extraction. First, clinical and radiological evaluations were performed on the patients. In the clinical evaluation, systemic status, tooth deficiency, occlusion and the status of the impacted tooth were evaluated. Panoramic film was taken for radiographic evaluation.

Inclusion criteria;

- Individuals aged 18 years and over,
- Patients with partially impacted wisdom teeth,
- Individuals with systemic status according to ASA classification as ASA0 and ASA1,
- Individuals who have not used any medication in the last two weeks,
- Individuals who do not have a missing lower second molar.

Exclusion criteria for the study;

- Individuals with mouth opening less than 25 mm for various reasons,
- Pregnant and breastfeeding individuals,
- Individuals who do not come to postoperative check-ups,
- Individuals using different medications other than the recommended medication.

Individuals who were allergic to the study drugs and the materials to be used were excluded from the study. All patients were included in the study after detailed information about the study was provided and a consent form was signed by the patient. The study was initiated after permission was obtained from the XXX University Ethics Committee. (Decision No:) All operations were performed by the same physician in the operating room of the XXX University Faculty of Dentistry, Department of Oral and Maxillofacial Surgery, adhering to surgical principles and sterilization rules, under equal operating conditions.

Study groups; Randomized, prospective, split mouth and single core, 30 patients in total were divided into two groups.

Study groups were determined as follows:

- A. Platelet-rich plasma (PRP) applied group.
- B. Low-level laser therapy (LLLT) applied group.

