First group (one side of the same patients): Platelet-rich plasma (PRP, initially 1200 revolutions per minute (rpm), 10 minutes later 2000 rpm for 10 minutes); second group (other side of the same patient): low-level laser treatment, diode laser (Ezlase 940; Biolase Technology, Inc., Irvine, CA) 100 mW (0.1 W) was applied for a total of 120 seconds. After the surgery, these two groups (methods) were applied to the extraction socket at different times (with a 2-week interval between each surgery). Both surgical sites were sutured with 3/0 silk suture (18 mm, 3\8 sharp, 75 cm black, Dağsan Silk Suture). It was randomly determined which material would be used first on which side. The other side was operated on after 2 weeks. Using an automatic centrifuge machine, PRP was initially prepared at 1200 rpm for 10 minutes and then 3 layers were created. 1) An upper straw-colored PPP (platelet-poor plasma). 2) A middle cloudy layer rich in platelets. 3) A lower layer rich in red blood cells. The straw-colored upper layer was collected together with the cloudy layer and centrifuged again at 2000 rpm for 10 minutes. Leukocyte-rich PRP was formed at the bottom of the test tube; the upper PPP was discarded using a pipette. 1 ml (10%) calcium chloride was added to the Platelet Rich Plasma for activation. (50 microliters of 10% calcium chloride is added for 1.0 mL of PRP). Gel was formed after 10 minutes. This layer consisting of approximately 2 ml of PRP was then placed in the extraction socket within 2 minutes after surgical removal of the mandibular third molar. The second group received a single session of intraoral 940 nm diode laser (BIOLASE) for 120 seconds immediately after suturing.

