The patients were checked in the first session they came to, and on the 2nd and 7th days after the operation. After the operation in all patients; Amoxicillin 1000mg (Largopen 1000mg,2*1 (Bilim Ilac Sanayii Ve Ticaret A.S. Istanbul, Turkey), Dexketoprofen 25mg (Arveles 25mg, 2*1 (Menarini, Istanbul, Turkey)), benzylamine HCl + chlorhexidine gluconate gargle (Andorex 200ml gargle, 3*1 (Humanis Sağlık A.S. Istanbul, Turkey) were used routinely. Sutures were removed after 1 week. Pain was assessed with Visual Analog Scale (VAS) at 3, 6, 9, 12 and 24 hours and on days 2, 3, 4, 5, 6 and 7. Angulus-tragus, angulus-lateral canthus, angulus-nasalis, angulus-labial commissure and angulus-pogonion points were used to evaluate edema. Measurements were made immediately before, 2 days after and 7 days after the operation. For the evaluation of trismus, mouth opening - the distance between the incisal edges of the central teeth during maximum mouth opening - was measured immediately before, 2 days after and 7 days after the operation. As a result, statistical analysis was performed and interpreted for the

obtained data. Before surgical extraction of the impacted tooth, the inferior alveolaris and buccal nerve were local anesthetized and the buccal flap was elevated mucoperiosteally with a 'Winter' incision using a scalpel number 15. A 1.6 mm diameter steel carbide round cutter, fissure cutter burs, a surgical micromotor operating at 1400 rpm and serum irrigation were used to remove the bone. The teeth were exposed. The teeth were then divided into two by bur and extracted with the help of a dental elevator. During the operation, 2 ampoules of local anesthetic (Ultracain 69 DS forte-Aventis İlaç Sanayi Tic. A1, Turkey) containing 40 mg/ml articaine HCl and 0.012 mg/ml epinephrine HCl were used as local anesthetic solution in all groups. The flap was closed primarily with 3/0, 19 mm atraumatic silk sutures and 3/8 round needles. The time between the first incision and the last suture was calculated and recorded.

Statistical Analysis Plan

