All statistical analyses were performed in a statistical software program (SPSS version 26.0, IBM Corp.). Mean, standard deviation, median, minimum and maximum values were calculated for descriptive statistics. Categorical data were shown with frequency and percentage. The conformity of the data to normal distribution was evaluated by examining the Shapiro-Wilk test and histograms. Comparisons between the two treatment groups were made with the Student-T test for data suitable for normal distribution, while the Mann-Whitney U test was used for data not suitable for normal distribution. In order to find statistical differences in the time-dependent changes in the measured data in both treatment groups, repeated measures ANOVA test was used for normally distributed data and Bonferroni test was used for post-hoc comparisons. Friedman test was applied to non-normally distributed data and Dunn-Bonferroni test was used for post-hoc comparisons. Chi-square test was applied for comparison of categorical data. Significance level was determined as $p<0.05$.

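### Plain Bonferroni is valid but needlessly conservative for the within-treatment time comparisons of the six outcomes measured at three times; a three-mean step-down rule keeps the same 5% familywise error and can test day 7 against pre-op at 0.05 instead of 0.0167

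*Combined protocol and SAP*

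**What the plan says.** The Study Protocol section sets three assessment times for both kinds of outcome. For the five facial distances: "Measurements were made immediately before, 2 days after and 7 days after the operation". Mouth opening "was measured immediately before, 2 days after and 7 days after the operation".

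The Statistical Analysis Plan section gives the purpose of the time comparisons: "In order to find statistical differences in the time-dependent changes in the measured data in both treatment groups". For normal data, "repeated measures ANOVA test was used for normally distributed data and Bonferroni test was used for post-hoc comparisons". For other data, "Friedman test was applied to non-normally distributed data and Dunn-Bonferroni test was used for post-hoc comparisons". The threshold is "Significance level was determined as $p<0.05", with sidedness not stated.

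The design is split mouth. Although "30 patients in total were divided into two groups", the treatment description makes clear that each patient supplies both sides: "First group (one side of the same patients" and so on. Each treatment therefore has 30 sides, one per patient.

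The plan names no step-down or closed procedure, does not state the number of pairs, and singles out no particular contrast. It gives no sample-size, power or effect-size calculation.

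**The concern.** Bonferroni divides the error rate as if all three equalities could still be true after one has been rejected. With three means they cannot: if one pair differs, at most one of the other two equalities can hold. The division by three is then stricter than 5% familywise control requires.

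The contrast most exposed is day 7 versus pre-op. A change at day 2 is plausible after bone removal and tooth sectioning, and if it is clear, its p-value passes 0.0167 easily. The day-7 contrast is then still held to 0.0167 with nothing gained against the 5% familywise limit. What is at stake is some avoidable loss of sensitivity in an analysis the SAP chose to plan, for up to six measures under two treatments.

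**Working it through.** The plan states no power or effect figure, so there is none to reproduce.

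**Inputs from the documents.** Level 0.05; three times (pre-op, day 2, day 7); 30 patients, each contributing one side per treatment.

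**Assumptions.** Two-sided tests, 30 complete pairs, 5% taken as the familywise level for each outcome within each treatment, paired t-tests for the pairs, and a clear day-2 change.

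**1. Level under the plan.** Three times give 3 × 2 / 2 = 3 pairs, so Bonferroni tests each at 0.05/3 = 0.0167.

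**2. Step-down rule (Shaffer's refinement of Holm).** Compare the smallest p with 0.05/3. If it passes, test the other two at 0.05; otherwise declare none. Only three situations are possible, because two true equalities force the third:
- All three equal: any false claim needs the smallest p to pass 0.05/3, with probability at most 3 × 0.05/3 = 0.05.
- Exactly one pair equal: a false claim needs that pair's p to pass 0.05, with probability at most 0.05.
- No pair equal: no false claim is possible.

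Familywise error is therefore at most 5%, and every pair rejected by Bonferroni is also rejected here.

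**3. Simulation check** (100,000 trials per scenario, n = 30; equal-variance and unequal-variance covariances):

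| Truth | Plain Bonferroni | Step-down |
|---|---|---|
| No time differs (familywise error) | 0.044; 0.039 | 0.044; 0.039 |
| Only day 2 differs (day-7 error) | 0.017; 0.016 | 0.051; 0.049 |

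The 0.051 is simulation noise around an exact 0.05: the standard error is √(0.05 × 0.95/100,000) = 0.0007.

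**4. Which results change.** With 29 degrees of freedom the critical t is 2.541 at 0.0167 and 2.045 at 0.05. Dividing by √30, the day-7 verdict differs only when the observed mean change lies between 0.464 and 0.373 SD of the paired difference.

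**5. Power for day 7 versus pre-op.** Noncentral t, 29 degrees of freedom, noncentrality d√30, where d is the true change in SDs of the paired difference. The documents give no value for d, so a range is shown:

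| d | At 0.0167 | At 0.05 | Gain (points) |
|---|---|---|---|
| 0.3 | 20.3% | 35.5% | 15.2 |
| 0.4 | 37.8% | 56.3% | 18.5 |
| 0.5 | 58.3% | 75.4% | 17.1 |
| 0.6 | 76.7% | 88.8% | 12.1 |
| 0.7 | 89.4% | 95.9% | 6.5 |
| 0.8 | 96.1% | 98.8% | 2.7 |

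The change detectable with 80% power falls from 0.62 to 0.53 SD.

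**6. Price across outcomes.** There are 6 measures × 2 treatments = 12 families. If day 7 equals pre-op in all of them and day 2 clearly differs, expected false day-7 claims go from 12 × 0.0167 = 0.2 to 12 × 0.05 = 0.6. If the families were independent, the chance of at least one goes from 1 − 0.9833^12 = 18% to 1 − 0.95^12 = 46%. Correlation between families would lower both chances.

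**The case against.** The strongest reply is that nothing here is wrong. Bonferroni after repeated measures ANOVA controls the error rate, and it comes with simple simultaneous intervals that a step-down rule does not supply. In a simulation of three pairwise intervals (n = 30, equal variances), joint coverage was 95.5% with t = 2.541 and 87.7% with t = 2.045. The SAP has no correction across outcomes, so some conservatism within each outcome has practical value. The trial's stated purpose is to compare PRP with laser, and these tests do not make that comparison. All of this stands, and it limits the point to one of efficiency. It does not remove the point: the SAP plans these tests, announces no simultaneous intervals that would be lost, and can be improved at almost no cost.

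A reader might infer several stronger things that the documents do not support:
- **That incomplete recovery will be missed.** Only p-values between 0.0167 and 0.05 change verdict; large residual changes are found either way.
- **That a non-significant day-7 result will be reported as full recovery.** The plan states no recovery criterion or claim. That misreading is also open under the step-down rule, which still misses a 0.4 SD change 44% of the time (100 − 56).
- **That Bonferroni costs this trial extra patients or needlessly wide intervals.** The number of patients is fixed with no stated sample-size calculation, and the extra interval width buys joint coverage.

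**Conclusion.** The point holds as lost efficiency in a valid analysis. For the five facial distances and mouth opening, plain Bonferroni holds every pair at 0.0167 where a rule with the same 5% familywise guarantee allows 0.05 after the first rejection. The 0.05 is conditional on that first rejection, and the 5% applies per outcome and per treatment, with no control across outcomes under either rule.

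The loss for day 7 versus pre-op is about 3 to 19 percentage points of power over true changes of 0.3 to 0.8 SD. The size rests on the assumed effect range, 30 complete pairs, two-sided tests and a clear day-2 change; the dominance of the step-down rule over Bonferroni does not. VAS pain is outside the argument, because its 11 times do not have the three-mean structure. This is a worthwhile refinement, not a flaw that threatens the trial's conclusions.

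**What to change.** Replace the post-hoc wording for the three-time outcomes in the Statistical Analysis Plan along these lines: within each outcome and treatment, compute the three unadjusted pairwise p-values; compare the smallest with 0.05/3; if it is significant, test the other two at 0.05 each; if not, declare none. Use paired t-tests in the normal branch.

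In the Friedman branch, apply the same rule to pairwise Wilcoxon signed-rank tests, so that both branches agree. Dunn comparisons do not suit the rule, because they use ranks from all three times and so do not test each pair separately. The three-mean logic carries over under the usual signed-rank assumption that paired differences are symmetric. Leave the VAS pain analysis as it is.

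State the downsides in the SAP: day-7 false positives of about 5% instead of 1.7% per outcome and treatment, no control across outcomes, and no matching simultaneous intervals. Report any day-7 estimate with its interval, labelled as unadjusted if it is, and say that non-significance is not evidence of recovery.

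The cost is a few sentences and a rule applied by hand to three p-values per family, with no new data. The document is written in the past tense, so if results have already been seen the change must be labelled post hoc.

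### PRP-versus-laser tests carry no multiplicity correction: up to 23 postoperative comparisons (15 if the facial distances are combined) are each judged at p<0.05, with no primary outcome to limit them

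*Combined protocol and SAP*

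**What the plan says.** The Statistical Analysis Plan describes two kinds of analysis of the measured outcomes.

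- **Between treatments.** "Comparisons between the two treatment groups were made with the Student-T test for data suitable for normal distribution", with Mann-Whitney U otherwise and chi-square for categorical data. No correction is attached to any of these tests.
- **Over time.** The stated aim is "In order to find statistical differences in the time-dependent changes in the measured data in both treatment groups". For normal data the method is a repeated measures ANOVA, after which "Bonferroni test was used for post-hoc comparisons"; for other data, "Friedman test was applied to non-normally distributed data and Dunn-Bonferroni test was used for post-hoc comparisons".

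The only decision rule is the closing sentence, "Significance level was determined as" p<0.05. The documents name no primary outcome, primary time point, testing order or global test.

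The Study Protocol sets the schedule. Pain is recorded by VAS "at 3, 6, 9, 12 and 24 hours and on days 2, 3, 4, 5, 6 and 7". Five facial distances and mouth opening are each measured before surgery and 2 and 7 days after it. Each of the 30 patients receives PRP on one side and laser on the other.

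**The concern.** The title poses a comparative question, and only the PRP-versus-laser tests answer it. Contrasts between times within a treatment describe recovery. The plan controls error for the recovery contrasts and leaves the treatment contrasts at 0.05 each, however many are run. Under that rule, one significant result at one pain time or for one facial distance may be reported as a difference between the treatments, and the plan gives no means of telling it from a chance finding.

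**Working it through.** The plan states no number of tests, familywise error or power, so there is no figure of its own to reproduce.

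**1. Count of postoperative treatment comparisons (Study Protocol schedule)**

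- Pain: 5 hourly + 6 daily = 11.
- Facial distances: 5 × 2 days = 10 if analysed singly, or 1 × 2 = 2 if combined.
- Mouth opening: 1 × 2 days = 2.
- Total: 11 + 10 + 2 = 23, or 11 + 2 + 2 = 15.

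Testing the 6 baseline values as well would give 29. Tests of operating time or of categorical variables would add more.

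**2. Independent tests, each of true size 0.05**

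Chance of at least one false positive = 1 − 0.95^k.

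- k = 15: 53.7%.
- k = 23: 69.3%, with 23 × 0.05 = 1.15 false positives expected.

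**3. Correlated outcomes, paired tests**

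The outcomes are correlated, but the documents give no values, so these are assumptions. The simulation used 30 pairs, normal data, no true difference, two-sided tests (the plan does not state sidedness) and three domains (pain, swelling, mouth opening). Repeat runs differ by one or two percentage points.

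| Correlation within / between domains | 23 tests | 15 tests |
|---|---|---|
| 0 / 0 | 69% | 54% |
| 0.5 / 0.2 | 54% | 42% |
| 0.8 / 0.4 | 34–35% | 29% |
| 0.9 / 0.5 | 26% | 22% |

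**4. The unpaired tests as written**

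With within-patient correlation ρ between the two sides, the mean difference has variance 2σ²(1 − ρ)/n. The unpaired test assumes 2σ²/n. Each test is therefore conservative when ρ > 0: its true size is about 5%, 2%, 0.7% and 0.1% at ρ = 0, 0.3, 0.5 and 0.7. Familywise error for 23 tests:

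| Within / between domains | ρ = 0 | ρ = 0.3 | ρ = 0.5 | ρ = 0.6 | ρ = 0.7 |
|---|---|---|---|---|---|
| 0.5 / 0.2 | 53% | 28% | 11–12% | about 5% | 1.7% |
| 0.8 / 0.4 | about 34% | 18% | 7% | 3.6% | 1.1% |

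Adding weaker outcome correlations widens the range to about 34–69% at ρ = 0 and 7–14% at ρ = 0.5.

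**5. After correction**

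Holm on the 23 paired tests gave a familywise error of 3–5% over outcome correlations from 0/0 to 0.8/0.4. The first Holm step uses 0.05/23 = 0.00217, or 0.05/15 = 0.00333 for 15 tests. From the noncentral t with n = 30 pairs and 80% power, the detectable difference, in SDs of the paired difference, is 0.53 at 0.05, 0.75 at 0.05/15 and 0.78 at 0.05/23.

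**The case against.** The strongest reply is that the inflated figures in step 3 belong to paired tests, while the plan specifies unpaired ones. Mouth opening is measured in the same person for both operations and the facial distances come from the same face, so high within-patient correlation is plausible for 12 of the 23 raw measurements (change scores could be less correlated). At ρ = 0.6 or above, familywise error under the plan as written is about 5% or less.

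This stands as a limit on the claim. A reader might infer that chance will often produce a significant difference under the written plan, or that error exceeds 5% whatever the correlation. The documents support neither. But where error is low, it is low only because the tests ignore the pairing, which also discards power. Once the split-mouth data are analysed as pairs, the inflation returns in full.

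A reader might also take 23 as a minimum. It is an inference from the schedule: the plan does not say that every time is tested, or that the five distances are analysed singly.

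Two further points are fair. Correcting post-hoc contrasts after an omnibus test is ordinary practice, so the Bonferroni step is not itself a mistake. And one named primary comparison would keep the primary error at 5%, with the rest secondary and with less loss of power. That is a legitimate alternative remedy, but the plan does not contain it.

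**Conclusion.** The concern holds in limited form. The stated decision rule does not control error for the trial's own comparative question: roughly 15 to 23 treatment comparisons are implied, none is corrected, and nothing ranks them. For a paired analysis, familywise error reaches 69% (23 independent tests) or 54% (15), and is about 29–54% across the two counts for outcome correlations of 0.5/0.2 to 0.8/0.4. For the unpaired tests as written it could lie anywhere from about 1% to 69%, depending on correlations that the documents do not give. These figures assume normal data, two-sided tests, 30 complete pairs and testing at every postoperative time. That the treatment tests are uncorrected does not depend on these assumptions; the size of the inflation does.

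**What to change.** Amend the Statistical Analysis Plan in these respects, together:

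1. Analyse PRP minus laser within patient, by paired t test or Wilcoxon signed-rank test. The correction should not be added without this step: Holm on the unpaired tests would tighten tests that may already be conservative.
2. State whether the five facial distances are analysed singly or combined, and define the postoperative treatment tests as one family of 23 or 15 accordingly. Settle this before looking at treatment differences.
3. Report adjusted p-values by Holm's step-down, or by a max-T permutation that flips the sign of each patient's whole vector of differences.
4. Claim a treatment difference only at adjusted p<0.05, and label unadjusted p-values as descriptive.

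The correction on time contrasts can stay, and every outcome and time is kept. The change needs wording and a few lines of analysis, but no new data.

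The cost is power. The paired difference detectable with 80% power at n = 30 rises from 0.53 SD to at most 0.78 SD (0.75 SD for 15 tests). Max-T is slightly milder, with a critical t of about 3.2–3.3 against 3.36 for Bonferroni over 23 tests.

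### After Friedman, the Dunn-Bonferroni test ignores the paired values of the two times compared, so it misses pain falls in every patient between times one or two ranks apart, and some consistent day-7 deficits

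*Combined protocol and SAP*

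**What the plan says.** The Statistical Analysis Plan sets out the within-treatment analyses of time course, whose purpose it gives as "In order to find statistical differences in the time-dependent changes in the measured data in both treatment groups". Data that pass the normality check (Shapiro-Wilk and histograms) go to repeated measures ANOVA with Bonferroni comparisons. For the rest, "Friedman test was applied to non-normally distributed data and Dunn-Bonferroni test was used for post-hoc comparisons". The plan does not limit which pairs of times are compared, and it names no paired alternative.

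The Study Protocol gives the number of times. For pain: "Pain was assessed with Visual Analog Scale (VAS) at 3, 6, 9, 12 and 24 hours and on days 2, 3", with daily readings continuing to the end of the week, which makes 11 times. For edema: "Measurements were made immediately before, 2 days after and 7 days after the operation". Mouth opening "was measured immediately before, 2 days after and 7 days after the operation". Edema and mouth opening therefore have three times each.

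The design is described as "Randomized, prospective, split mouth and single core, 30 patients in total were divided into two groups". The next paragraph makes clear that each patient has PRP on one side and laser on the other, so each treatment has 30 patients' series.

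**The concern.** A post-hoc comparison asks whether two particular times differ within a treatment. Dunn's test after Friedman answers through mean ranks taken over all k times, with a fixed standard error that is correct only if all k times are exchangeable. That is not a plausible null for healing data: pain falls over the week, and day 2 is expected to differ clearly from baseline. The result for two times then depends on how many other times were measured and where they fall. In a trending series, the assumed variance of a difference between neighbouring ranks is far too large, and real changes are missed.

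At stake is the description of when pain falls and whether function has recovered. A non-significant comparison of day 7 with the preoperative value could be read as recovery while most patients remain below their own baseline.

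**Working it through.** The documents give no power or effect-size figure for these comparisons, so there is none to reproduce.

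**Inputs.** n = 30 patients per treatment (split mouth). k = 11 for pain, so 11 × 10 / 2 = 55 pairs. k = 3 for edema and mouth opening, so 3 pairs. Alpha is 0.05. Assumptions: two-sided tests, all pairs compared, no tie correction.

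**Formula.** z = (difference of mean ranks) / sqrt(k(k+1)/(6n)). The two-sided p is multiplied by the number of pairs.

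**Pain, k = 11.**
- Standard error: sqrt(132/180) = 0.856 ranks.
- Critical z at 0.05/55 is 3.317, so the required gap is 3.317 × 0.856 = 2.84 mean ranks. Without any adjustment it is 1.96 × 0.856 = 1.68.

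| Fall in all 30 patients | z | p | p × 55 |
|---|---|---|---|
| 1 rank | 1.17 | 0.243 | 1.0 (capped) |
| 2 ranks | 2.34 | 0.0195 | 1.0 (capped) |
| 3 ranks | 3.50 | 0.00046 | 0.025 |
| 10 ranks (3 h to day 7 in a steady decline) | 11.7 | <0.0001 | <0.0001 |

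If pain falls at every step in every patient, the 10 neighbouring pairs and the 9 two-step pairs are missed: 19 of 55. The other 36 are detected. For the same data, tests that use only the two times compared, with the same 55-fold adjustment, give:
- exact sign test: 2/2^30 = 1.9e-9, adjusted 1.0e-7;
- Wilcoxon signed-rank (normal approximation): z = 4.78, adjusted 9.5e-5.

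If the description of the groups were taken to mean 15 patients per treatment, the required gap would be 4.02 ranks, and 34 of 55 pairs would be missed.

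**Mouth opening or edema, k = 3.**
- Standard error: sqrt(12/180) = 0.258. Critical z at 0.05/3 is 2.394, so the required gap is 0.618 ranks.
- A one-rank change in all 30 patients gives z = 3.87, adjusted p = 0.0003. It is detected.
- Now let day 2 be the extreme value in every patient, and let x of 30 patients remain worse on day 7 than before surgery. The day-7 versus preoperative gap is (x − (30 − x))/30.

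| x of 30 | Gap | z | Dunn p × 3 | Sign test p × 3 |
|---|---|---|---|---|
| 21 | 0.400 | 1.55 | 0.36 | 0.13 |
| 22 | 0.467 | 1.81 | 0.21 | 0.048 |
| 23 | 0.533 | 2.07 | 0.12 | 0.016 |
| 24 | 0.600 | 2.32 | 0.060 | 0.004 |
| 25 | 0.667 | 2.58 | 0.029 | 0.001 |

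The two methods disagree at 22 to 24 patients. Below that neither is significant; above it both are.

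**Power under assumed values.** The documents give no means or SDs, so these figures only illustrate.
- Pain falling 0.6 VAS points per time (between-patient SD 1.2, within-patient SD 0.8, AR(1) 0.6): Dunn-Bonferroni against Bonferroni signed-rank was 0% against 69% for neighbouring times and 0.1% against 99.7% two steps apart. Dunn power was about 54% at three steps and 100% at four or more.
- Mouth opening with assumed means of 45, 32 and 43 mm and within-patient SD 2 mm: separate simulation runs gave Dunn 23% to 30% against 89% to 92% for day 7 versus preoperative. With a 1.5 mm deficit it was about 8% against 62% to 64%. With a 3 mm deficit Dunn reached about 77%, and with 5 mm 99.8%.

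**Error rate of the replacement.** Holm-adjusted signed-rank tests rejected the day-7 pair in about 4.7% of runs under full recovery. Under a flat curve their familywise rate was about 1%.

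**The case against.** Dunn-Bonferroni after Friedman is a recognised procedure, and it stays within its nominal level when the curve is flat. The comparisons that it misses are within one treatment and mostly between neighbouring times. Whether 6 hours differs from 9 hours under PRP does not decide between PRP and laser. The loss arises only if an outcome is judged non-normal. That is plausible for late-week VAS, which is bounded at zero, but the plan does not settle it in advance, and mouth opening and facial distances are continuous lengths that may well pass the check. All of this stands, and it limits the point to a secondary, conditional loss.

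A reader might infer that with 11 times and 30 patients the test cannot detect any pain fall, even one that occurs in every patient. The arithmetic does not support that: a unanimous three-rank fall has adjusted p = 0.025, and 36 of 55 pairs in a steady decline are detected. A reader might also infer that the trial will report false recovery on day 7. That needs the Friedman branch and a modest deficit; larger deficits are found.

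The objection does not remove the defect for close pain times, where the test fails whatever the consistency of the change. Nor does it remove it for the 22-to-24-patient window with three times, which is arithmetic once day 2 is taken as extreme in every patient.

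**Conclusion.** The point holds within limits. Under the Friedman branch, the planned post-hoc test cannot declare significant a pain change whose mean-rank gap is below 2.84, even when all 30 patients change. For mouth opening and edema the loss is narrower; its size beyond the counted cases depends on means and SDs that the documents do not give.

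The effect is confined to within-treatment statements about time course. The documents give no ground for extending it to the PRP-laser comparison, which uses other tests, or to the Friedman test itself. The conclusion assumes two-sided tests, all pairs compared and no tie correction. It is a cheap improvement that should be made.

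**What to change.** Replace the Dunn-Bonferroni part of the sentence in the Statistical Analysis Plan with:

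> After a significant Friedman test, pairs of times are compared within each treatment by the Wilcoxon signed-rank test on the paired values, with Holm adjustment over the pairs tested.

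Report the median paired change for each pair.

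The cost is one sentence and no new data. There are two small downsides. The Holm adjustment has to be applied by hand. Late VAS values near zero will also produce ties and zero differences, so exact p-values, or the sign test, should be used where these are many.
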